23.0 Appendix 3 Statistical analysis plan

Sample size and randomisation

We have assumed that a sample size of 3000 is feasible and that this is likely to be distributed as 750 in the "low response/no response" group and 2250 in the "normal response" group. We might then wish to estimate what difference between these two groups we could detect with 90% power. We have good estimates from previous studies over time in vulnerable populations and have therefore considered a range of infection and hospitalisation rates that might be plausible for this group. We have also considered the statistically most conservative option by setting the proportion at 50%.

In all cases, we can detect an absolute difference between groups of less than 10% and often less than 5% even for the rarer outcome of hospitalisation. These are consistent with a standardised effect sizes ranging from 0.15 to 0.36 for infection, which are consistent with small to moderate effects. The effect size for hospitalisation is less certain and ranges from 0.24 consistent with a small effect through to 1.33, a very large effect.

We consider this reassuring as it indicates that for a wide range of scenarios, we should have adequate power in the whole cohort for our primary outcome of infection and we may have power to detect a moderate effect for the rarer secondary outcome of hospitalisation, depending on the prevailing population rates and the variant of interest.

We will monitor all the assumptions that underlie these calculations at least monthly and will discuss monthly at our Trial Meeting Groups, if there are any concerns about power for key analyses.

Randomisation procedure

This is an observational cohort and participants will not be randomised. The cohort may be used in future to recruit to randomised trials and the process for selection and randomisation would be described accordingly in the associated trial protocol.

Statistical analysis considerations

Definition of analysis populations

CV groups are defined below and are derived in part from the QCOVID4 risk groups.

The Healthy Control (HC) group represent a population sampled from the PITCH Study (Protective immunity from T-cells in healthcare workers).

Baseline characteristics

At baseline the following characteristics will be described for the study cohort:

- Demographics (Age, BMI, self-reported ethnicity, sex, Index of Multiple Deprivation)

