Assuming serology is predictive of outcome, we will build a model to explore the predictive value of key patient data and the added value of serological results. We will explore the discrimination and calibration of a model only including baseline and behavioural variables compared to this model also including serological response. Discrimination will be determined by Harrell's C statistic and calibration will be determined by the predicted probabilities for infection. It is not possible to externally validate this model in this study; instead 1000 bootstrapped samples will be used in determining the 95% confidence intervals for the C statistic.

As a sensitivity analysis we will also consider serological response as a continuous variable. We will also consider time to first infection as a time to event outcome with death as a competing risk. This will be implemented in Stata using the *stcrreg* command. The same covariates will be included in the adjusted model as for the primary analysis. Unadjusted and adjusted analyses will present hazard ratios with 95% confidence intervals.

To assess the additive value of serological responses to CV status in predicting severe outcome We will undertake an analysis using the same modelling approach as for the primary outcome but with a composite outcome of severe infection (infection, hospitalisation or death).

Secondary Outcomes

To evaluate the serological vaccine responses of CV patients to new vaccines

28-day post vaccine (Visit 3) IgG antibody levels (BAU/ml) will be reported in HC and CV individuals. The proportion of combined and individual CV groups with no, low or normal Visit 3 antibody levels will be reported.

The median (IQR) of Visit 3 antibody levels in each CV group will be reported, alongside the values for HC.

Logistic regression models will be used to assess factors that contribute to serological response as a binary outcome with normal compared to lack of response (no/low). The model will include the baseline variables set out in **Section 5.2** and further variables may be added to the model if evidence emerges that such variable impacts on vaccine responses to vaccines. Univariable logistic regression will be used to explore the unadjusted relationship of each variable with the outcome and multivariable logistic regression will be used to explore the independent relationship of each variable with the outcome. We will report odds ratios and 95% confidence intervals for all models.

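### The bootstrap serves only an interval around the apparent C statistic, so optimism stays in C and calibration and the 95% interval sits too high

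*Protocol*

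**What the plan says.** Protocol, 23.0 Appendix 3, Primary Outcome. If serology proves predictive, the plan compares "a model only including baseline and behavioural variables compared to this model also including serological response". The performance measures follow: "Discrimination will be determined by Harrell's C statistic and calibration will be determined by the predicted probabilities for infection". On validation against outside data it states: "It is not possible to externally validate this model in this study". What it offers as the substitute is an interval: "instead 1000 bootstrapped samples will be used in determining the 95% confidence intervals for the C statistic".

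Appendix 3 attaches no optimism correction, shrinkage, cross-validation or other internal validation to C, and no resampling to calibration. It does not say whether the models are refitted in each resample. The approach carries over to the next outcome: "We will undertake an analysis using the same modelling approach as for the primary outcome but with a composite outcome of severe infection". The general principles call for complete-case analysis without imputation, which reduces the number of patients available to the model.

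**The concern.** The connecting word in the validation sentence puts a confidence interval where validation would otherwise stand. The two answer different questions. An interval says how far C might vary from sample to sample. Validation says how far C falls when the fitted model meets new patients. A model fitted and judged on the same patients looks better than it is, and an interval built around that figure inherits the bias.

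Calibration has a similar weakness. It is read from the predicted probabilities in the development data, where an unpenalised logistic model matches the observed risk on average and has slope 1 whatever the degree of overfitting.

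At stake are the absolute C of each model, its calibration and the individual predicted risks. A reader who wants to know how well patient data plus serology separate those who will be infected would get too favourable an answer, with error bars that look more reassuring than they should.

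**Working it through.** **Inputs from the protocol.** The cohort is 3000, assumed to split into 750 low or no responders and 2250 normal responders; power is 90%, two-sided alpha 5%; there are 1000 resamples. The plan states no C, interval or calibration figure that could be reproduced. The nearest checkable figure is the lowest standardised effect for infection, 0.15. At a 50% rate, 750 against 2250 gives a detectable difference of 6.8 points. The odds ratio is (0.5681/0.4319)/(0.5/0.5) = 1.32, and ln(OR) × √3/π = 0.151, which matches.

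**Number of parameters.** The plan gives none. The baseline list has about 12 items (age, BMI, ethnicity, sex, deprivation, occupation, nature of work, protective equipment, medical conditions, immunosuppression, vaccination history, prior infection). The household-illness variables add about 5 (timing, symptoms, severity, duration, number of contacts ill). At one parameter each that is 17. If the 20 groups of Table 2 enter as 19 indicators in place of the medical-conditions item, it is 16 + 19 = 35. A range of 10 to 40 is therefore used.

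**Simulation.** All inputs below are assumptions: normally distributed covariates, a covariate signal of 0.6 to 0.8 on the logit scale, 60 to 100 datasets per row and 100 resamples each. True C is the C of the fitted model in 100,000 new subjects. Optimism = apparent C − true C, computed before rounding. Coverage is the share of datasets whose interval contains the true C. Fixed means that only C is resampled; refit means that the model is refitted in each resample.

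| n | Parameters | Infected | Apparent C | True C | Optimism | CI half-width | Coverage, fixed | Coverage, refit | Slope in new subjects |
|---|---|---|---|---|---|---|---|---|---|
| 3000 | 10 | 30% | 0.662 | 0.654 | 0.009 | 0.020 | 84% | 76% | 0.95 |
| 3000 | 15 | 20% | 0.710 | 0.698 | 0.012 | 0.022 | 82% | 66% | 0.93 |
| 3000 | 30 | 30% | 0.668 | 0.647 | 0.021 | 0.020 | 49% | 11% | 0.86 |
| 3000 | 30 | 20% | 0.672 | 0.649 | 0.023 | 0.023 | 55% | 7% | 0.85 |
| 2000 | 40 | 20% | 0.686 | 0.635 | 0.051 | 0.027 | 8% | 0% | 0.70 |

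A repeat simulation over 10 to 40 parameters gave fixed-prediction coverage from 70% down to 8%, so the upper end is itself uncertain.

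**Hand check.** With bias b and standard error s = half-width/1.96, coverage ≈ Φ(1.96 − b/s) − Φ(−1.96 − b/s).
- Row 1: s = 0.0102, b/s = 0.88, coverage ≈ 86%.
- Row 4: s = 0.0117, b/s = 1.96, coverage ≈ 50%.
- Row 5: s = 0.0138, b/s = 3.70, coverage ≈ 4%.

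These agree with 84%, 55% and 8%, given that the Monte Carlo standard error of a coverage near 50% from 80 datasets is about √(0.55 × 0.45/80) = 0.056.

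**Calibration.** Maximum likelihood sets Σ(y − p̂) = 0 and Σx(y − p̂) = 0 for every covariate x. Regressing y on the fitted linear predictor in the same data therefore returns intercept 0 and slope 1. The last column shows what that conceals.

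**Gain in C from serology.** Thirty covariates plus one binary term with 25% low (750/3000), using the smallest odds ratio detectable at 90% power; apparent against true gain:
- 20% infected, OR 1.38: 0.0042 against 0.0044.
- 10% infected, OR 1.52: 0.0075 against 0.0074.
- 2% events, OR 2.22: 0.015 against 0.021.
- 20% infected, OR 1.0: 0.0004 against −0.0004.

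The gain is not materially inflated in any of these.

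**Same resamples used for optimism correction.** In row order, corrected C is 0.656, 0.700, 0.648, 0.647 and 0.642, within 0.007 of the true value each time. Coverage of the shifted interval is 93%, 89%, 93%, 91% and 87%.

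**The case against.** Several points on the other side stand. The primary analysis is an odds ratio, and the prediction model is conditional on serology being predictive and described as exploratory. The added value of serology, which is the headed aim, is hardly biased. Every input that drives the size is assumed; with few parameters and common infection the optimism is about 0.01. Calibration in the development data is not worthless either: the plan does not name slope as its measure, and predicted against observed risk, grouped or plotted, could still show non-linearity or other misfit.

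That a fuller analysis plan may supply the detail is a weaker defence. Section 11.0 refers to Appendix 3 as the statistical analysis plan, and the appendix fixes both the number of resamples and their purpose. The defence does cover the absent interval for the difference in C, since the general principles promise 95% intervals where applicable.

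A reader might infer two stronger claims. One is that the interval will exclude the true C. The plan states no interval, and under favourable assumptions most intervals still contain the true value. The other is that the damage is greatest for the severe outcome because events are few. As written, that composite counts infection alongside hospitalisation and death, so its events cannot be fewer than the infections.

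**Conclusion.** The point holds in a limited form. A stated method is given a task it cannot do: the interval takes the place of validation but leaves optimism untouched. C is biased upward for both models, and the interval is centred too high and under-covers.

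With 2000 to 3000 patients and 20 to 30% infected, optimism is about 0.01 with 10 to 15 parameters, with coverage about 65 to 84% depending on how the interval is built. With 30 to 40 parameters it is about 0.02 to 0.05, with fixed-prediction coverage about 8 to 55% and lower if models are refitted. These figures rest on assumed parameter counts, infection rates and signal strength.

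The harm is to absolute C, calibration and predicted risks. The primary odds ratio is not touched, and the gain in C from serology is largely unaffected. The change should be made before the model is built.

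**What to change.** Give the same 1000 resamples a second use. In each, repeat the full model-building for the models with and without serology, evaluate each refit in the resample and in the original data, and average the difference. Subtract that average from the apparent values. Report optimism-corrected C and calibration slope for both models, and build the 95% interval around the corrected C. Add a bootstrap interval for the difference in C, since that answers the added-value question. State the number of candidate parameters and say that models are refitted. Keep a plot of predicted against observed risk to look for misfit. Coefficient shrinkage is optional.

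No new data or extra resamples are needed, only the refits. The reported C becomes less favourable. With few events the correction is only partial: with 30 parameters and a 2% event rate (60 events in 3000), corrected C was 0.690 against a true 0.666, with 82% coverage. That would matter if a rarer outcome were modelled in the same way.

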Different antibody tests have been used for these studies; to ensure this analysis is transferable across assays, the WHO International Standard will be used to compare platforms. Descriptive statistics will set out the geometric mean titres of IgG antibodies by age, gender, disease type and treatment, and compared with control cohorts within the included studies. Preliminary analysis of the association between antibody concentration and effectiveness will include post-vaccination (≥3rd dose) antibody status in immunosuppressed people-antibody status will be considered as a binary value (detectable versus absent). Clinical outcomes of interest will include infection, hospitalisation and death; first considered as a composite, and then individually, data allowing. The odds ratio of clinical outcome by antibody status will be reported both unadjusted and adjusted for key participant (or patient − terms used interchangeably) characteristics. We will also explore the relationship between antibody concentrations as a continuous variable and clinical outcomes, with estimation of discriminative cut points at concentration levels associated with inferior effectiveness. A repeat analysis will be performed on non-immunosuppressed vulnerable people within these cohorts. Those groups with inadequate response with respect to the clinical outcomes as determined by these analyses would be included in the prospective study.

Data sharing and transfer: We will request ethical approval to use existing data from other studies to achieve the aims of STRAVINSKY. This will enable the development of data transfer arrangements between the existing studies with the STRAVINSKY team. Before doing this the data transfer arrangements will ensure the correct ethical approvals are in place and patients have consented for their data to be used in future ethically approved studies. The data transferred will be at patient level but will be completely anonymised. Data will be stored on secure servers at all times and transferred using encrypted files.

TABLE 1. Examples of studies to be included in the retrospective meta-analysis

Study	Patient Cohort	Numbers of participants
OCTAVE	Rheumatology, Solid Organ	2,686
	Transplants, Renal, Liver, Stem	
	cell Transplant	
OCTAVE-DUO	Rheumatology, Solid Organ	804
	Transplants, Renal, Liver, Stem	
	cell Transplant, lymphoma,	
	antibody deficiency	
PROSECO	Immunodeficiency	592
COVAD	Immunodeficiency	562
CORONACANCER	Cancer	3,555

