4.2 Objectives

Primary objectives:

a) To define and assess the predictive value of SARS-CoV-2 spike serology measurements for COVID-19 clinical outcomes (infection rates and disease severity) in CV people.

Secondary objectives:

- a) To evaluate the serological vaccine responses (magnitude and durability) of CV patients to bivalent or other vaccines given during the study period.
- b) To assess the functional activity of anti-spike IgG antibodies against new SARS-CoV-2 variants in CV patients during the study period.

Exploratory objectives:

- a) To evaluate alternate methods to predict COVID-19 infection/hospitalisation should antibody testing fail to predict relevant clinical outcomes (e.g. QCOVID4 score and T cell responses).
- b) To understand whether the serology vaccine response, in those with suboptimal responses to primary course, can be further enhanced with increasing doses of vaccination. \Box
- c) To assess T-cell response to emerging VoC in CV individuals.
- d) To determine the correlation between antibody and T-cell responses

Version: 2.0 26.11.2023 IRAS:325967

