- · Occupation, nature of work and type of personal protective equipment used during that work
- Medical conditions (self- reported)
- latrogenic immunosuppression (or within 6 months of iatrogenic immunosuppression including chemotherapy)
- · Vaccination history including COVID-19, influenza, and any test vaccines given
- · Known prior infection

Behavioural variables

If the participant self-isolated as a result of an illness in a household contact, we will collect data on the nature of that illness (when was illness, symptoms, severity, duration) and how many other household contacts were unwell.

Serological response

Time points for serological measurements: Assessment at 4 timepoints (Visit 1: baseline visit, Visit 2: before next vaccine dose, visit 3: 4 weeks post vaccine dose and Visit 4: 24-36 weeks post vaccine).

ii) 'Low' antibody range: Antibody values which lie within the lower 10th percentile of range of IgG antibody concentrations in HC following vaccine dose.

General analysis principles

- Summary statistics will include either mean, standard deviation, and/or median, interquartile range for continuous variables as appropriate to the distribution and n (%) for frequencies.
- The amount of missing data will be reported. Analysis will be of complete data and missing data will not be imputed.
- 5% two-sided level of statistical significance, with corresponding 95% confidence intervals presented where applicable.
- No adjustments for multiplicity are planned.

Planned analyses and reporting:

Primary Outcome

To assess the additive value of serological responses to CV status in predicting infection

The binary infection outcome will be captured by recording the timing and incidence rates of all infections from ≥14 days post vaccination given between Visit 2 until Visit 4 will be reported in the total combined CV groups, and by individual CV groups. We will describe the number and proportion of infections for each level of antibody response post-V3 (no, low, normal)

The primary analysis will be undertaken using a logistic regression model with infection as the outcome and antibody response post-V3 as a binary variable as the exposure. We will present odds ratios with 95% confidence intervals for the unadjusted model, as well as for a model adjusted for the baseline and behavioural variables as well as any COVID-19 therapy received in the community, preadmission and in hospital (where data available).

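### The composite for severe outcome is met by any infection, so the planned severity model cannot separate prediction of severe disease from prediction of infection

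*Protocol*

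**What the plan says.** The primary objective (protocol section 4.2) is to assess the predictive value of spike serology "for COVID-19 clinical outcomes (infection rates and disease severity) in CV people". It therefore has two parts.

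Appendix 3 gives each part its own analysis. For infection, the primary analysis is a "logistic regression model with infection as the outcome and antibody response post-V3 as a binary variable as the exposure". For severity, the stated aim is "To assess the additive value of serological responses to CV status in predicting severe outcome". That analysis takes over the primary modelling approach, "but with a composite outcome of severe infection (infection, hospitalisation or death".

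The sample size text of the same appendix treats hospitalisation as a separate and less frequent event: "we may have power to detect a moderate effect for the rarer secondary outcome of hospitalisation". It gives standardised effects of 0.15 to 0.36 for infection and 0.24 to 1.33 for hospitalisation.

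Appendix 5 holds a severity score from 0 to 7. Asymptomatic infection scores 1, admission for COVID-19 without oxygen scores 4 and death scores 7. No analysis in Appendix 3 refers to this score.

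**The concern.** An outcome meant to capture severe disease should leave out people who were infected but not severely ill. This one lets them in through its first component, which carries no severity qualifier. An analyst following the text would code a participant with a positive test and no symptoms as a severe event.

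Two wrong conclusions become possible. An association of antibody level with mild infection could be reported as prediction of severe disease. Conversely, a real association with hospitalisation or death could disappear because non-severe infections dominate the events. The second matters particularly here, because the protocol's own background (section 2.0) says that current vaccines protect against severe disease more than against infection.

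**Working it through.** **1. The definition.** Let I be infection, H hospitalisation and D death. The outcome as written is I or H or D.

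- If H and D are COVID-19-related, both lie inside I. The composite equals I, the primary outcome.
- If H and D are all-cause, the composite equals I plus hospitalisations and deaths in people without infection. These are not severe COVID-19 either.

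Appendix 3 qualifies neither word. Under both readings every member of I is an event. This step needs no assumed rates.

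**2. The plan's own figure.** Inputs from Appendix 3: 750 low or no responders (n1), 2250 normal responders (n2), 90% power, 5% two-sided, most conservative base rate 50%. For rates p1 and p2,

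power = Φ[(|p1 − p2| − 1.96·se0)/se1],

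where se0 = √[p̄(1 − p̄)(1/n1 + 1/n2)], p̄ is the pooled rate, and se1 = √[p1(1 − p1)/n1 + p2(1 − p2)/n2].

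Solving for 90% power at p2 = 50% gives p1 = 56.8%, a difference of 6.8 points and an odds ratio (OR) of 1.315. The standardised effect is ln(1.315)·√3/π = 0.151. This agrees with the stated 0.15 and with the statement that differences under 10% are detectable. The base rates behind the other ends of the stated ranges are not shown.

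**3. Share of composite events that are not severe** (COVID-19-related reading): 1 − p(severe)/p(infection). The rates are assumptions.

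| Infected | 1% hospitalised or dying of COVID-19 | 3% |
|---|---|---|
| 10% | 1 − 0.01/0.10 = 90% | 1 − 0.03/0.10 = 70% |
| 20% | 1 − 0.01/0.20 = 95% | 1 − 0.03/0.20 = 85% |
| 50% | 1 − 0.01/0.50 = 98% | 1 − 0.03/0.50 = 94% |

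**4. What the composite can hide** (assumed rates, COVID-19-related reading). Infection is 20% in both antibody groups; hospitalisation is 3% with low or no response and 1% with normal response.

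- Composite: 20% against 20%, OR 1.0.
- Hospitalisation alone: (0.03/0.97)/(0.01/0.99) = 3.06, with 93.5% power by the formula in step 2.

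The reverse case: infection 25.7% against 20%, hospitalisation 1% in both groups.

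- Composite: (0.257/0.743)/(0.20/0.80) = 1.38, with 90% power.
- Hospitalisation alone: OR 1.0.

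**5. A wider grid that allows some deaths without infection.** Assumptions: infection 10-50% in both groups; 1-5% of infected normal responders hospitalised, and three times that among low or no responders; 1% of uninfected participants die in both groups. The composite rate is infection + (1 − infection)·0.01, for example 0.20 + 0.80·0.01 = 20.8%. Across the grid 92-99% of composite events are infections and 1.4-7.4% involve hospitalisation. The composite shows no difference between groups, while hospitalisation alone has between 29% and nearly 100% power.

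**6. Where else Appendix 3 analyses hospitalisation.**

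- Subgroup analyses: counts of COVID-19-related hospitalisation, and exploratory models if numbers allow.
- QCOVID4: a whole-cohort logistic model of hospitalisation and death with the risk score as exposure. Serology is added only if the score discriminates and calibrates well.
- Mucosal antibodies: an exploratory logistic analysis that includes hospitalisation.

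None of these is an unconditional whole-cohort model of Visit 3 serology with hospitalisation or death as the outcome.

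**The case against.** The strongest reply is that the parenthesis is a drafting slip and that severity is covered elsewhere. A slip is plausible. But Appendix 3 does not leave the outcome open for a later document: it fixes it, and nothing else in the protocol corrects it. The coverage elsewhere is real, and it limits the point in four ways.

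- A reader might infer that the study cannot address severity at all, or that no whole-cohort model uses hospitalisation. The documents do not support that: the QCOVID4 model uses hospitalisation and death for all participants and may go on to test serology. The defect belongs to one planned model.
- A reader might infer that the composite adds only non-COVID deaths. That takes hospitalisation as COVID-19-related and death as all-cause, whereas the text qualifies neither.
- A reader might infer that the severity and infection odds ratios must nearly coincide. They coincide under the COVID-19-related reading. Under the all-cause reading the added events could be unevenly spread between antibody groups and move the estimate, though not towards measuring COVID-19 severity.
- A reader might extend the criticism to the retrospective analysis in section 3.0: "Clinical outcomes of interest will include infection, hospitalisation and death; first considered as a composite, and then individually, data allowing". That composite is not labelled severe, and its components are then to be analysed separately where the data allow. It needs no change.

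It is also fair to say that the percentages rest on assumed rates. The logical defect does not.

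**Conclusion.** The point holds, limited to the severe-outcome model in Appendix 3. As written, that model repeats the infection analysis, with at most some infection-free hospitalisations or deaths added. It conflicts with the severity part of the primary objective and with the sample size text, which treats hospitalisation as a distinct outcome. It should be corrected before analysis, because following the text would give a wrong severity result and the other analyses of hospitalisation do not replace it.

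This conclusion rests on the definition alone. Its numerical size rests on rates that the protocol does not give: 85-95% of composite events not severe at 20% infected, and 70-98% over 10-50% infected, in each case with 1-3% hospitalised or dying of COVID-19. These figures are illustrative.

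**What to change.** In Appendix 3, remove plain infection from the severe composite, so that the outcome is COVID-19 hospitalisation or COVID-19-related death. State how each component is attributed to COVID-19. State which Appendix 5 levels count as severe. That mapping needs care: the column that appears to cover hospital-acquired infection seems to grade the middle scores by symptoms and oxygen rather than by admission, and the top score is death without attribution.

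The change is a few sentences and needs an attribution rule, but no new visits or samples. The cost is precision. With 750 against 2250 and 90% power (unadjusted two-proportion approximation), the detectable rates are:

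| Assumed rate, normal response | Detectable rate, low or no response | OR |
|---|---|---|
| 5% | 8.4% | 1.73 |
| 2% | 4.3% | 2.22 |
| 1% | 2.8% | 2.86 |
| 0.5% | 1.9% | 3.93 |
| 0.1% | 1.1% | 10.8 |

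The standardised effects run from 0.30 to 1.31, within the 0.24 to 1.33 that the protocol already states for hospitalisation. The wider interval is the precision the study really has for severity. With few events, a short covariate set or penalised (Firth) logistic regression may help, but that is optional and not part of the correction.
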